5.2.9 Evaluation Visit II (V8, 12 week \pm 7 days after the V6)

5.2.9.1 Review patients voiding diary for urinary frequency, functional bladder capacity, and record reported UAB symptom score, and GRA.

5.2.9.2 Vital signs monitoring and record adverse events.

5.2.9.3 Check urinalysis for urinary tract infection if patient has symptoms suggestive of urinary tract infection.

5.2.9.4 Perform Uroflowmetry study for maximum flow rate, urodynamic study and PVR volume.

5.2.9.5 Collect 30 ml urine for analysis of the urinary NGF and cytokines levels.

5.3. Withdrawal Criteria

Patients with any of the following conditions may be withdrawn from the trial:

5.3.1. Patients decide to withdraw their consent at any time-point.

5.3.2. Patients indicate the status of lack of efficacy which is of clinical significance judged by the investigators that may lead to permanent damage to the patients.

5.3.3. Investigators consider that there is of safety concerns for the patients to remain in the trial (such as development severe medical disease).

5.3.4. Lost of follow-up or death.

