7.2 Analysis

The statistical objective of this study is to demonstrate that the efficacy of ESWT is superior to placebo with respect to the decreases of UAB symptom score, and PVR. The safety profile of ESWT or placebo for the either group of treatment of patients with DU/UAB will also be confirmed.

Primary Efficacy Endpoint

The efficacy of ESWT treatment will be evaluated for:

(1) Net changes of the mean post void residual (PVR) volume (mL) from baseline to 1 month after the treatment day.

Secondary Efficacy Endpoint

The efficacy of ESWT will be evaluated for:

- (1) Net change of the following parameters from baseline to 1 month after the treatment day: functional bladder capacity (FBC), voiding frequency at daytime and voiding frequency at night time, incontinence, as record in 3-day voiding diary.
- (2) Global response assessment (GRA) of satisfaction by the patient (categorized into -3, -2, -1, 0, 1, 2, 3, indicating markedly worse to markedly improved) at 1 month after the treatment day. An improvement of GRA by 2 scales at 1 month is considered effective.
- (3) Net changes of the maximum flow rate, voided volume, Pdet@Qmax, and postvoid residual volume from baseline to 1 month after the treatment day.
- (4) Changes of Underactive Bladder Questionnaire (UAB-Q) score.
- (5) Changes of urinary nerve growth factor and cytokines level from baseline to 1 month after treatment day.

Voiding frequency at daytime and nighttime is measured as mean of the three-day voiding diary preceding the scheduled visit and the record days are 3 days.

Net change of each efficacy item will be analyzed by paired t-test between baseline and post-treatment in the treatment group and controlled group. The net changes of each efficacy item will be analyzed by ANOVA test to compare between treatment group and controlled groups. The global response assessment by the patients will be analyzed by Fisher exact test between the treatment and controlled groups.

All efficacy variables will be reported of respective point estimated and 95% confidence interval. Comparison tests will be reported of respective p value.

Secondary Safety Endpoints

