7.3. Estimation of Incomplete Data

Due to this relatively small scale of clinical trial, any incomplete observation will be considered as missing data with no specific estimation for the incomplete data.

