7.4 Sample Size

We used PASS 14 to calculate power for this study. Group sample sizes of 24 and 24 achieve 80.677% power to reject the null hypothesis of equal means when the population mean difference (Net changes of the mean post void residual (PVR) volume (mL) from baseline to 1 month after the treatment day) is -50.0 with a standard deviation for both groups of 60.0 and with a significance level (alpha) of 0.050 using a two-sided two-sample equal-variance t-test. According to 20% of the patient's drop-out rate, the number of subjects is set to 60, and the evaluator is 48 to get enough verification power.

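### A patient withdrawn for lack of efficacy before V7 has no GRA and becomes missing under SAP 7.3, so a judged failure leaves the responder comparison although SAP 7.1 keeps that patient in ITT

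*Protocol*

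**What the plan says.** SAP 7.2 makes the GRA a responder endpoint: "An improvement of GRA by 2 scales at 1 month is considered effective". The arms are compared with Fisher's exact test. No denominator is stated, and nothing says how to count a patient without a GRA. Protocol section 2 defines the same endpoint again at 3 months.

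Protocol 5.2 lists the GRA only at V7 (4 weeks after V6) and V8 (12 weeks after V6). The treatment visits V1 to V6 do not include it, and no early-termination assessment is described.

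Protocol 5.3.2 permits withdrawal when "Patients indicate the status of lack of efficacy which is of clinical significance judged by the investigators", limited by its closing clause to cases that could cause permanent harm. Protocol 6.1 adds that, by default, a deterioration that might be either an adverse event or treatment failure is classed as lack of efficacy.

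SAP 7.3 sets one rule for all variables and all reasons: "any incomplete observation will be considered as missing data with no specific estimation for the incomplete data".

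SAP 7.1 defines ITT as patients with baseline screening and treatment, requires no post-treatment value, and bases the main conclusions for primary and secondary endpoints on ITT. The per-protocol set requires a post-treatment evaluation of the primary endpoint.

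**The concern.** For most missing values the outcome is unknown, and a small trial may reasonably decline to estimate it. A 5.3.2 withdrawal is different, because the reason for leaving is an investigator's judgement that the treatment has failed. On a yes/no effectiveness endpoint that is usable outcome information, and SAP 7.3 discards it.

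The reported figure then becomes a response rate among patients who stayed long enough to be asked, under an ITT label. The per-protocol analysis is no cross-check, since a patient who leaves before V7 has no 1-month evaluation and is outside that set too. SAP 7.1 and 7.3 also point to different denominators for the GRA. Unless that is settled before unblinding, the choice could be made with results in hand.

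**Working it through.** **Step 1: the plan's own figures.** SAP 7.4 states "Group sample sizes of 24 and 24 achieve 80.677% power to reject the null hypothesis of equal means", where the mean difference "is -50.0 with a standard deviation for both groups of 60.0", "with a significance level (alpha) of 0.050" and "using a two-sided two-sample equal-variance t-test".

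- Noncentrality = 50 / (60 × √(1/24 + 1/24)) = 50 / 17.32 = 2.887, with 46 degrees of freedom. The noncentral t distribution gives power 80.677%, an exact match.
- Dropout: "According to 20% of the patient's drop-out rate, the number of subjects is set to 60". 48 / (1 − 0.20) = 60, also a match. With 1:1 allocation this is 30 per arm enrolled and 24 evaluable.

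These figures concern PVR. The documents give no response rate, power or sample size for the GRA.

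**Step 2: can a failure leave before any GRA?** V6 is at week 5 and V7 is four weeks later, so the first GRA falls about nine weeks after first treatment. A 5.3.2 withdrawal in that interval leaves no GRA. A withdrawal between V7 and V8 leaves the 1-month GRA intact and loses only the 3-month one.

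**Step 3: effect within one arm.** Let n be the patients treated, r the responders, and w the lack-of-efficacy withdrawals before the GRA, all non-responders.

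- Scored as not effective: r/n.
- Treated as missing: r/(n − w).
- Ratio: n/(n − w).

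With n = 30: w = 2 gives 30/28 = 1.07; w = 3 gives 30/27 = 1.11; w = 6 (all of a 20% dropout in that arm) gives 30/24 = 1.25.

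**Step 4: effect on the comparison.** The change in the difference is (r_E/n) × w_E/(n − w_E) − (r_P/n) × w_P/(n − w_P), where E is ESWT and P is placebo. Its sign depends on the split of withdrawals. For illustration, assume 15 and 6 responders of 30. The documents supply neither these rates nor the values of w. Total loss is at most 12 of 60, the planned 20%.

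| Withdrawn (ESWT, placebo) | Observed rates | Difference (points) | Fisher p |
|---|---|---|---|
| Scored as not effective, any split | 15/30 = 50.0%, 6/30 = 20.0% | 30.0 | 0.029 |
| 2, 2 | 15/28 = 53.6%, 6/28 = 21.4% | 32.1 | 0.026 |
| 3, 3 | 15/27 = 55.6%, 6/27 = 22.2% | 33.3 | 0.024 |
| 6, 6 | 15/24 = 62.5%, 6/24 = 25.0% | 37.5 | 0.019 |
| 10, 2 | 15/20 = 75.0%, 6/28 = 21.4% | 53.6 | not needed |
| 4, 8 | 15/26 = 57.7%, 6/22 = 27.3% | 30.4 | 0.045 |
| 2, 10 | 15/28 = 53.6%, 6/20 = 30.0% | 23.6 | 0.144 |
| 0, 12 | 15/30 = 50.0%, 6/18 = 33.3% | 16.7 | 0.369 |

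Equal loss, or more loss on ESWT, widens the difference. A moderate placebo excess (4, 8) leaves it almost unchanged, and a large one shrinks it. The rows with 10 or 12 in one arm exceed 20% for that arm and show direction only.

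**The case against.** **This route may be rarely used.** Withdrawal under 5.3.2 is discretionary and tied to possible permanent harm, so it is much narrower than ordinary non-response. Visits V2 to V6 schedule no efficacy assessment, and Protocol section 2 offers repeat treatment to patients not effective at 3 months, which is a reason to stay. This stands. The number could be small or zero, and nothing supports attributing the whole 20% dropout to lack of efficacy. The factor 1.25 is a bound. Protocol 6.1 pulls slightly the other way by classing ambiguous deteriorations as lack of efficacy.

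**A reader might infer that the rule exaggerates the benefit of ESWT.** The documents do not support that. If ESWT works, lack-of-efficacy withdrawals should be commoner on placebo, and dropping enough of them hides benefit.

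**A reader might also infer that significance would change.** That depends on chosen counts. 15/24 against 7/24 gives p = 0.041 and the same patients as 15/30 against 7/30 give p = 0.060, but those sit at the boundary. With 12 and 6 responders (40% and 20% of 30), equal loss of 6 per arm gives p = 0.135 against 0.158, and nothing flips.

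**The GRA is the patient's rating at 1 month, whereas 5.3.2 rests on an earlier investigator judgement.** This is fair. Scoring the patient as not effective is a convention. It still keeps more relevant information than treating the patient as missing.

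**Why not score every missing GRA as a failure?** For safety withdrawals, withdrawn consent and loss to follow-up, the outcome is not known. Blanket failure scoring there is a debatable choice and belongs in a sensitivity analysis.

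**The small trial justifies SAP 7.3.** Size is a reason not to estimate unknown values. It does not justify discarding a recorded reason for failure.

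**Conclusion.** The gap is real, and it is conditional. Read together, Protocol 5.2 and 5.3.2 and SAP 7.3 remove a judged failure from the GRA comparison while SAP 7.1 keeps that patient in ITT, and no text says which prevails. Where such withdrawals occur, each arm's response rate is overstated by n/(n − w): about 7% in relative terms for 2 of 30, 11% for 3 of 30, and 25% if all of a 20% dropout in that arm were lack of efficacy. This assumes that those withdrawn would not have been responders.

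The direction of bias in the between-arm difference cannot be fixed in advance. The 1-month GRA is affected only by withdrawal before V7, the 3-month GRA by withdrawal before V8. The GRA is a secondary endpoint, and the PVR sample size and power are untouched. The change is worth making because it is cheap and settles the denominator before results are known.

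**What to change.** In SAP 7.2, Secondary Efficacy Endpoint (2), state the following:

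- In the ITT analysis of the GRA at 1 month, a patient withdrawn before that evaluation for lack of efficacy under Protocol 5.3.2 is scored as not effective and kept in the denominator. SAP 7.3 does not apply to these patients. The same rule holds for the 3-month GRA.
- A sensitivity analysis scores all other missing GRA values (safety withdrawal, withdrawn consent, loss to follow-up) as not effective.
- The observed-case result is reported alongside.

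The cost is a few sentences before unblinding. No new assessment is needed, provided the reason for each withdrawal is recorded, and the sample size does not change. There are two small downsides: reported response rates become slightly less favourable, and in those few cases an investigator's judgement stands in for the patient's own rating.

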5.4. Concomitant Treatments

Investigator will try to minimize the concomitant medications for the patients during the trial duration.

Currently taking medication(s) that may affect urination, including prescription drugs (i.e. anticholinergics, tricyclic antidepressants, bethanechol), over the counter drugs, dietary and/or herbal supplements, adrenergic antagonists. Alpha adrenergic blockers are allowed to use in a stable condition (longer than 1 month and keeping use during the study period).

6. ADVERSE EVENTS

6.1. Introduction

An adverse event is defined as a new medical condition or worsening of the existing condition following or during the trial medicinal exposure (including placebo). However, a deterioration of medical condition can be in doubt of either an adverse event or being due to the lack of efficacy of the treatment. Situations as such should be considered as a lack of efficacy unless the sponsor or the investigators or the regulatory authorities state to the contrary.

All adverse events occurring during the study should be documented on Adverse Event Forms. One Adverse Event Form should be filled out for each adverse event. All items on the form should be completed and feedback to National Reporting System of Adverse Drug Reaction in Taiwan (ADR) as soon as possible. For serious adverse events, a preliminary Adverse Event Form must be returned to the ADR immediately (within 24 hours), with complete and/or new information submitted to the ADR as soon as it becomes known.

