2. OBJECTIVE AND ENDPOINTS

The objective of this study is to evaluate the efficacy and safety of ESWT for the treatment of DU/UAB.

The primary and secondary endpoints are described as shown below:

(1) Primary End-point (1 month)

The efficacy of LESW will be evaluated for:

Net changes of the mean post void residual (PVR) volume (mL) from baseline to 1 month after the treatment day.

(2) Secondary end-points

Efficacy

The efficacy of ESWT will be evaluated for:

- (1) Net changes of the following parameters from baseline to 1 month after the treatment day: functional bladder capacity (FBC), voiding frequency at daytime and voiding frequency at night time, incontinence, as record in 3-day voiding diary.
- (2) Global response assessment (GRA) of satisfaction by the patient (categorized into -3, -2, -1, 0, 1, 2, 3, indicating markedly worse to markedly improved) at 1 month after the last treatment day. An improvement of GRA by 2 scales at 1 months is considered effective.
- (3) Net changes of the maximum flow rate, voided volume, Pdet@Qmax, and postvoid residual volume from baseline to 1 month after the treatment day.

(4) Changes of Underactive Bladder Questionnaire (UAB-Q) score.

(5) Changes of urinary nerve growth factor and cytokines level from baseline to 1 month after treatment day.

Safety

(1) Local adverse event incidences (hematuria, miction pain, UTI, urinary retention). The severity of adverse event is categorized as indicated below:

Severity of AE	Description
Mild	Transient and easily tolerable, not affecting usual daily activities
Moderate	Causes patient's discomfort, interrupting usual daily activities
Severe	Causes considerable interference with daily activities and may be incapacitating or life-threatening

(2) Systemic Adverse Events:

Any systemic adverse event occurring after ESWT will be asked to report and patients will be properly investigated and treated. The cause for systemic adverse event may be not related with ESWT.

(3) Changes in physical examinations.

(4) Changes in blood pressure and other laboratory test results will be examined if patients have severe adverse events or physical examinations reveal abnormalities.

(3) Follow-up (3 months)

Efficacy

The efficacy of ESWT will be evaluated for:

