- (1) Net changes of the following parameters from baseline to 3 month after the treatment day: functional bladder capacity (FBC), voiding frequency at daytime and voiding frequency at night time, incontinence, as recorded in 3-day voiding diary.
- (2) Global response assessment (GRA) of satisfaction by the patient (categorized into -3, -2, -1, 0, 1, 2, 3, indicating markedly worse to markedly improved) at 3 month after the last treatment day. An improvement of GRA by 2 scales at 3 months is considered effective.
- (3) Net changes of the maximum flow rate, voided volume, Pdet@Qmax, and postvoid residual volume from baseline to 3 months after the treatment day.
- (4) Changes of Underactive Bladder Questionnaire (UAB-Q) score.
- (5) Changes of urinary nerve growth factor and cytokines level from baseline to 3 months after treatment day.

Patients who are not effective to the treatment at 3 months will receive repeated ESWT treatment.

Safety

- (1) Local adverse event incidences (hematuria, miction pain, UTI, urinary retention) are reported.
- (2) Any systemic adverse event occurring after ESWT will be asked to report and patients will be properly investigated and treated. The cause for systemic adverse event may be not related with ESWT treatment.

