4.2. Inclusion Criteria

Patients must meet all the following criteria to be eligible to enter the trial:

- 4.2.1. Adult male or female, at least 20 years of age.
- 4.2.2. History of UAB (defined as bothersome chronic incomplete bladder emptying) for at least 3 months documented in the medical record with recurring UAB symptoms.
- 4.2.3. No UAB symptom relief (unresponsiveness) with previous used medications and/or other treatments.
- 4.2.4. Voiding difficulty (complains of difficulty emptying the bladder).
- 4.2.5. UAB consistent with diabetes, MS, Parkinson's disease, or aging idiopathic.
- 4.2.6. Post void residual ≥ 100 mL.
- 4.2.7. Bladder capacity > 200 mL and < 800 mL.
- 4.2.8. Pressure flow Urodynamic testing demonstrating impaired detrusor contractility or areflexia without evidence of BOO, with maximum detrusor pressure Pdet at Qmax (Pdet@Qmax) of < 20 cmH₂O and Maximum flow rate (Qmax) < 15 mL/sec for female and BCI <100 and BOOI < 40 for male [2, 3].
- 4.2.9. Total UAB Questionnaire Score ≥ 3 .
- 4.2.10. Females of child-bearing potential agree to use reliable birth control for the entire study duration.
- 4.2.11. Willing and capable of understanding and complying with all requirements of the protocol, including proper completion of the voiding diaries and self-administered questionnaires.
- 4.2.12. Free of active urinary tract infection.
- 4.2.13. Free of bladder outlet obstruction on enrollment.
- 4.2.14. Patient or his/her legally acceptable representative has signed the written informed consent form.
- 4.2.15. Subject on clean intermittent catheterization (CIC) should have been on CIC for at least 1 month and should be able to void spontaneously and not be completely dependent on CIC.

4.3.Exclusion Criteria

- 4.3.1. Female patients who is pregnant, lactating, plans to become pregnant, or with child-bearing potential without contraception.
- 4.3.2. Simultaneously participating in another investigational drug or device study or use of any investigational drug(s) or therapeutic device(s) within 3 months preceding enrollment.
- 4.3.3. Has been treated with an investigational device, drug, or procedure for UAB within the last 3 months.
- 4.3.4. History of cancer in pelvic organs, ureters, or kidneys or any cancer that has undergone treatment within the past 12 months.

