- (1) Local adverse event incidences (hematuria, micturition pain, UTI, urinary retention) will be reported by both treatment group and controlled group and by physiological systems as appropriate. Incidence of adverse events and the categories of adverse event severity between treatments will be analyzed. The coding system used will be COSTART.
- (2) The abnormalities of laboratory test results will be reported by patient list in the patients who have been tested for having severe adverse event.
- (3) The changes in physical examinations will be presented in the by-patient list.
- (4) All statistical tests used will be two-tailed with α = 0.05.

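### Section 6.1's lack-of-efficacy default is not reconciled with the naming of urinary retention as a local adverse event, so non-serious retention can be under-counted in both arms

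*Protocol*

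**What the plan says.** Protocol 6.1 starts from a broad definition: "An adverse event is defined as a new medical condition or worsening of the existing condition following or during the trial medicinal exposure". It then narrows this for a deterioration that is in doubt between an adverse event and lack of efficacy: "Situations as such should be considered as a lack of efficacy unless the sponsor or the investigators or the regulatory authorities state to the contrary". The duty to complete a form attaches to adverse events: "All adverse events occurring during the study should be documented on Adverse Event Forms".

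Protocol Section 2 lists four local events as safety endpoints at 1 month, and again at 3 months: "Local adverse event incidences (hematuria, miction pain, UTI, urinary retention) are reported". The severity table in Section 2 has a mild grade that includes transient events. SAP 7.2 repeats the list by arm, "Local adverse event incidences (hematuria, micturition pain, UTI, urinary retention) will be reported by both treatment group and controlled group", and adds that incidence and severity will be analysed between treatments.

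On the disease itself, Protocol 4.2.2 requires "History of UAB (defined as bothersome chronic incomplete bladder emptying) for at least 3 months" and 4.2.6 requires "Post void residual ≥ 100 mL". The primary efficacy endpoint is the change in post-void residual to 1 month.

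**The concern.** Urinary retention is the named local event that lies closest to the disease under study. A patient enrolled for incomplete emptying who then has more trouble emptying may be seen as having an adverse event or as not responding. That is the doubt 6.1 describes, and its default resolves it against counting an adverse event. Section 2 and SAP 7.2 meanwhile promise an incidence for the same event.

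At stake is one named safety result in a trial whose objective covers safety as well as efficacy. Followed as written, the default can remove cases from that incidence without any departure from the protocol.

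**Working it through.** **Step 1. The texts side by side.**

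| Question | Protocol 6.1 | Protocol Section 2 and SAP 7.2 |
|---|---|---|
| Is worsening of the existing condition an adverse event? | Yes by definition, but lack of efficacy by default if in doubt | Not addressed in general |
| Is urinary retention an adverse event? | Not mentioned, not exempted | Yes, named as a local adverse event |
| Do transient events count? | Not addressed | Yes, the mild grade includes them |
| Which rule prevails? | Not stated | Not stated |

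**Step 2. Can retention be in doubt?** Under 4.2.2 and 4.2.6 every participant enters with chronic incomplete emptying and a residual of at least 100 mL. Neither document says what separates retention as an event from a change in residual volume. Retention can therefore be read as worsening of the studied condition, which is enough to bring it within the default.

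**Step 3. Where the default acts.** It acts on classification, not detection. Adverse events are recorded at both evaluation visits (5.2.8.2, 5.2.9.2), and 5.1 lists adverse event recording among the visit assessments. An episode can be reported at a visit and still be classed as lack of efficacy. It then needs no form and does not enter the SAP 7.2 incidence.

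**Step 4. What one event is worth.** The inputs are the 48 evaluable patients and 20% drop-out in SAP 7.4, and the 1:1 allocation in Protocol Section 3.
- Enrolment: 48 / (1 − 0.20) = 60, which reproduces the plan's figure.
- Per arm: 60 / 2 = 30.
- One patient with an uncounted event: 1 / 30 = 3.3 percentage points of that arm's incidence.

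**Step 5. Illustration on assumed values.** The documents give neither a retention rate p nor the share s of cases classed as lack of efficacy. The values of p and s below are assumptions, not estimates. The recorded rate is p(1 − s), and the chance that an arm of 30 records no retention is (1 − p(1 − s))^30.

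| Assumed p | s = 0 | s = 0.5 | s = 1 |
|---|---|---|---|
| 5% | 0.95^30 = 21% | 0.975^30 = 47% | 100% |
| 10% | 0.90^30 = 4% | 0.95^30 = 21% | 100% |
| 20% | 0.80^30 = 0.1% | 0.90^30 = 4% | 100% |

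With s = 0, meaning investigators count every case, nothing is lost. The effect runs from none to complete loss, depending on a share that the documents do not fix.

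**Step 6. Direction across arms.** The default is the same in both arms, and Protocol 3.2 blinds the investigator. If the same share s were lost in each arm, a true difference p1 − p2 would be recorded as (1 − s)(p1 − p2) and the ratio p1/p2 would not change. Nothing in the documents shows that s would differ by arm.

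**The case against.** The strongest reply is that 6.1 gives way on its own terms. It covers only doubtful cases, and it yields when the sponsor or investigators say otherwise. Naming retention as a local adverse event at both time points in Section 2 and again in SAP 7.2 can be read as saying otherwise, and as the specific rule over the general one. This is a fair reading and it limits the size of the problem. It does not remove it: no text states the exemption or ranks the two rules, and no criterion guides the override. If nobody acts, the default stands.

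A second reply is that an episode that starts and resolves is unlikely to be mistaken for lack of efficacy, while persistent worsening would show in the residual volume at the evaluation visits. The first half narrows the exposed cases. The second does not restore the count, because a residual volume is not an adverse event incidence.

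A third reply is that 6.2 defines non-serious events broadly and that the opening sentence of 6.3 may catch serious cases. For serious cases this largely stands, although the outcome list in 6.3 first requires that the event be called an adverse event. The point is therefore confined to non-serious retention. For those cases the breadth of 6.2 helps but does not displace the default in 6.1.

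A reader might go further and infer a flat contradiction, a bias in favour of one arm, or damage to the primary result. The documents support none of these. The two rules can be read together, the default treats both arms alike under blinding, and it does not alter how residual volume is measured or analysed.

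**Conclusion.** The point holds as a minor one. Section 6.1 states an active default, Section 2 and SAP 7.2 state an expected count, and the studied disease makes retention an event to which both can apply. Non-serious retention can be under-counted in both arms.

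The conclusion assumes that some retention will be judged doubtful and that the override will not be used every time. The documents neither establish nor exclude this. The size is therefore unknown beyond the 3.3 percentage points per uncounted patient at about 30 per arm. The plan's sample size and primary conclusion do not depend on it.

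**What to change.** Reconcile 6.1 with Section 2 and SAP 7.2. Add one sentence to 6.1 stating that urinary retention, as a named local adverse event, is always recorded and counted as an adverse event, whether or not it is also judged lack of efficacy. The same sentence may cover hematuria, pain on voiding and urinary tract infection for consistency, although the doubt is argued here for retention only.

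Optionally, list by arm the deteriorations classed as lack of efficacy, so that a reader can see how often the default was used.

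The cost is one sentence and, if wanted, one listing, with no new procedure for patients. The downside is a somewhat higher reported adverse event rate in both arms, since some worsening of the disease will be counted as an adverse event.
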